## 8.3 LOST TO FOLLOW-UP

A patient will be considered lost to follow-up if he or she fails to return an assessment and study staff are unable to contact the participant after at least 3 attempts.

The following actions will be taken if a patient fails to return to the clinic for a required study visit:

- Staff will attempt to contact the participant, reschedule the missed intervention within 10 days, counsel the participant on the importance of maintaining the assigned visit schedule and determine if the participant wishes to and/or should continue in the study
- Before a participant is deemed lost to follow-up, the investigator or staff will make every effort to regain contact with the participant (where possible, 3 telephone calls and check-in at upcoming cancer care visit, and if necessary, a certified letter to the participant's last known mailing address). These contact attempts will be documented in the participant tracking log.
- Should the participant continue to be unreachable, he or she will be considered to have withdrawn from the study with a primary reason of lost to follow-up.

## 9 STUDY ASSESSMENTS AND PROCEDURES

## 9.1 ENDPOINT AND OTHER NON-SAFETY ASSESSMENTS

**Screening.** We will build a master list form in REDCap linking patient names, MRNs, and study IDs. We will build a separate REDCap form for screening. The eligibility screening form will include patient screener ID, date screened, date must be enrolled by (21 day window), eligibility criteria (e.g., performance status, time on cancer treatment, age, etc.), whether the patient is being rescreened for eligibility, and, if rescreened, the last date of screening. If deemed potentially eligible, additional fields will appear in the eligibility database for tracking dates of upcoming appointments and contact with patients. Patients must be enrolled within 21 days of screening or else they will need to be rescreened.

**Administration of Questionnaires.** Patient-reported measures related to a future efficacy trial and of treatment processes were chosen based on their validity and sensitivity to change in cancer patients and recommendation for clinical trials. These measures will be completed by patients pre-intervention (TP0), ~4 weeks after baseline (T1), and post-intervention (~8-weeks after T0; TP2) on paper, online (REDCap), or by phone. For patients who use MyChart®, a link to the REDCap survey will be provided through a study research message delivered in MyChart®. Patients will use a participation ID on their questionnaires. If more than 30 days pass between baseline and participant viewing the mPal tool, key sections (e.g., palliative care knowledge, palliative care use) of the baseline questionnaire will be re-administered prior to viewing mPal. See **Table 2** for a list of measures to be administered, psychometric properties, assessment schedule, and role in analysis plan. All patient-reported measures will be entered in REDCap in the REDCap project built for those patients who enroll.

**Interviews.** Patients assigned to mPal (n = 20-40) will complete two interviews. The interviews will last approximately 10-15 minutes and will query overall satisfaction with the intervention, perceived impact of mPal on clinical care, and reasons patients chose or chose not to talk with their doctor about their palliative care needs. The interviews will take place over the phone, Zoom, or in-person, according to patient preference. Interviews will be conducted by the study team and audiorecorded. After each interview, the interviewer will write up observations in the form of field notes, which will include information about the setting (e.g., details about room if in-person vs. on the phone), personal environment (e.g., respondent's attitude and openness), social environment (e.g., presence of caregiver or others in room), and summary of patient's responses. Recordings will be transcribed verbatim, the transcripts checked for accuracy and deidentified.

**Table 2. Aim 1 and 2 Measures**

Construct	Description	Data Sources	Level		Schedule
			Pt	Pv/Sy	
Aim 1. Implementation Outcomes					
Feasibility	FIM  : 4 item implementation measure of intervention feasibility ( $\alpha = .89$ ); Individual interviews (pts, pvs)	Survey; interviews	X	X	mPal Patients: T1 Providers: T3
Acceptability	AIM  : 4 item implementation measure of intervention acceptability ( $\alpha = .85$ ) individual interviews (pts, pvs)	Survey; interviews	X	X	mPal Patients: T1 Providers: T3
Aim 2. Effectiveness and Equity Outcomes related to Planned Future Trial					
PC referral	Proportion of patients in each arm who receive a referral to PC within 1-month (survey) and 3-months (EHR) post-mPal intervention	EHR, Survey	X	X	Patients: T2 (survey); System: 3-months post intervention (EHR)
PC knowledge	HINTS PC  : 10 items; assesses self-reported PC knowledge and PC perceptions. PACKS	Survey	X	X	Patients: T0, T1 (mPal only), T2 Providers: T0, T1, T3
Motivation to use PC	PCAS-9  : 9 items; assesses emotional, cognitive, and behavioral components of motivation to use PC ( $\alpha$ 's = .70-.90)	Survey	X	X	Patients: T0, T1 (mPal only), T2 Providers: T0, T1, T3
Opportunities to use PC	5 items; perceived ability to access PC. Based on preliminary study and literature. 	Survey,	X	X	Patients: T0, T2 Providers: T0, T3
PC discussion	2 survey items; Interview questions to supplement (experiences discussing PC during clinical encounters, quality of discussion, how mPal was used)	Survey, depth interviews	X	X	Patients: T0, T2 Providers: T0, T3
Demographics	15 items; sociodemographics, health literacy  (pts), PC training (providers)	Survey	X	X	Patients: T0 Providers: T0
Equity	Characteristics of mPal patients who do/do not seek PC referral and do/do not show knowledge increase; Interview with those who do/do not use PC; barriers	Survey, interviews	X	X	mPal Patients: T2, 3m post intervention

Note. Pt = Patient; PV = provider; Sy = System; T = timepoint; T0 = baseline; T1 = post mPal app viewing or knowledge check (pt assessment); post webinar viewing (providers); T2 = 8-week follow-up (pt assessment); T3 = post-patient-level intervention period (for providers)

**Review of Existing Data in EHR.** As part of the consent, all patients will be asked to consent to a HIPAA release for permission to collect the following protected health information for up to 12 months post-enrollment:

- age
- gender
- racial/ethnic data
- zip code
- mailing address, email, phone number (for participant payments)
- lung cancer diagnosis (includes histology and stage)
- date started lung cancer treatment
- type of treatments received
- medical record number

- ECOG/Karnofsky performance status
- referrals for palliative care, palliative care consultations completed, referrals to other supportive care services (e.g., Social Work), dates of referrals and consultations
- Documentation of advance care planning/advance directive
- mPal palliative care screener results (for repeated screenings)

This information will be collected by study staff and entered in REDCap or obtained through clinical informatics service.

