**Study Description and Objectives:**

This is a pilot RCT (40 patients mPal; 40 patients usual care; 6 providers not randomized) to test the feasibility and acceptability of a multilevel implementation strategy for outpatient palliative care (PC).

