## 1.2 SCHEMA

**Note.** T0 = baseline; T1 = assessment (~3-4 weeks after baseline); T2 = 8±3 week follow-up (after T0); T3 = ~3-month post-mpal implementation

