**A.3. Overcoming barriers to PC implementation is a multilevel problem.** Unfortunately, factors at the patient, provider, and healthcare system level lead to underutilization of PC (Fig. 1). Less than 15% of patients who could benefit from PC utilize it. Most patients have poor PC knowledge (i.e., do not know what palliative care is or what concerns it can address, equate PC with end of life, and/or fear using it means stopping cancer treatment), will not seek PC without a provider recommending it, and under-report PC concerns to their oncology team (see Preliminary Data). Providers often also have poor PC knowledge (i.e., do not understand how PC can help manage patient concerns during treatment, equate it with end of life), are uncertain how to talk about PC with patients, and face time constraints during clinic visits to assess and address PC needs. Most healthcare systems rely on providers to refer patients to PC, yet do not have systems in place to help identify appropriate patients and facilitate referrals. Collectively, barriers to PC utilization fall into determinants of knowledge, motivation, and opportunity (Fig. 1).

[figure not shown]

Figure 1. Conceptual Model of PC Implementation Problem

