## 6.3 MEASURES TO MINIMIZE BIAS: RANDOMIZATION AND BLINDING

This is a randomized controlled trial design (patient-level randomization). Study staff and patients will not be blinded to allocation; however, study staff and patients will not know allocation until after a patient has completed the baseline questionnaire. The statistician will generate the randomization table, which will be implemented through REDCap.

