### 7 STUDY CONTROL CONDITION

#### 7.1 CONTROL CONDITION DESCRIPTION

Only the patient level component of mPal is randomized. Patients not randomized to the mPal patient implementation strategies will receive usual care.

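### The 1-month PC referral proportion rests on unblinded patient self-report, so its ascertainment may differ by arm; the dated EHR referrals already collected should replace it

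*Combined protocol and SAP*

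**What the plan says.** The PC referral row of Table 2 (section 9.1) defines the outcome as "Proportion of patients in each arm who receive a referral to PC within 1-month (survey) and 3-months (EHR) post-mPal intervention" and schedules it as "Patients: T2 (survey); System: 3-months post intervention (EHR". The patient survey thus supplies the early reading and the EHR the later one. Section 4.1, by contrast, gives the EHR as the only source for referrals.

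On timing, section 1.2 has "T2 = 8±3 week follow-up (after T0" and puts T1 about 3-4 weeks after baseline. The note under Table 2 places the patient T1 after viewing of the mPal tool.

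On what differs between arms, section 7.1 states "Only the patient level component of mPal is randomized". Section 6.1.1 describes that component as a PC education video with a knowledge check, followed by a needs screener. Section 6.3 says "Study staff and patients will not be blinded to allocation". Section 2.2 says "Most patients have poor PC knowledge (i.e., do not know what palliative care is or what concerns it can address".

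On the alternative source, section 9.1 (Review of Existing Data in EHR) covers, for all consenting patients and up to 12 months after enrolment, "referrals for palliative care, palliative care consultations completed, referrals to other supportive care services (e.g., Social Work), dates of referrals and consultations".

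Section 3 says that no formal effectiveness hypotheses are tested. Section 10.4.3 plans to correlate changes in PC knowledge and motivation with changes in referrals, without naming the referral source. The documents give neither the wording of the referral item nor any check of survey answers against the EHR.

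**The concern.** To report a referral correctly, a patient has to know that the service offered was palliative care. That is the knowledge the randomised component is built to change. With the same true referral rate in both arms, the reported rates can still separate because one arm is better at naming what happened. This can occur even if the plan is followed to the letter.

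Three further features weaken the early reading:

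- The T2 window is set from baseline, while the outcome is set from the intervention, so the two need not coincide.
- A control patient has no intervention date, so the one-month clock has no starting point in that arm.
- If self-report feeds the correlation in section 10.4.3, better knowledge can itself raise reporting. A positive correlation could then appear without any change in referral behaviour.

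At stake is the early referral estimate that the pilot hands to the planned trial.

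**Working it through.** **Plan's own figure.** None is stated for the referral outcome. Section 10.2 gives 80 patients for estimating enrolment and retention, with no power, effect size or interval width, so there is nothing to reproduce. The arm sizes come from the synopsis: "40 patients mPal; 40 patients usual care; 6 providers not randomized".

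**Model.** For each arm, reported rate = p × s + (1 − p) × f. Here p is the true referral rate, s the share of referred patients who report it, and f the share of non-referred patients who report one. The documents give none of these. The nearest figure is in section 2.1, that less than 15% of these patients receive PC. That is receipt, not early referral, so p = 15% is an assumption.

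**Step 1: recognition only (f = 0, same p in both arms).** The spurious difference is p × (s in mPal − s in control).

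- s = 0.90 v 0.60: 15% × 0.90 = 13.5% v 15% × 0.60 = 9.0%, a difference of +4.5 points.
- s = 0.95 v 0.80: 15% × 0.95 = 14.25% v 15% × 0.80 = 12.0%, a difference of +2.25 points.
- With the same two pairs, p = 5% gives +0.75 to +1.5 points and p = 30% gives +4.5 to +9.0 points.

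**Step 2: false positives (p = 15%, s = 0.90 v 0.60).**

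- Controls count other supportive services as PC, f = 0.02 mPal v 0.10 control: (13.5 + 1.7) − (9.0 + 8.5) = 15.2 − 17.5 = −2.3 points. The sign reverses.
- mPal patients report their own request in the tool as a referral, f = 0.10 mPal v 0.02 control: (13.5 + 8.5) − (9.0 + 1.7) = 22.0 − 10.7 = +11.3 points.
- Break-even: an excess false-positive rate in controls of 0.15 × 0.30 / 0.85 = 5.3 points cancels the recognition bias.

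**Step 3: precision.** At 15% in each arm of 40, the SE of the difference is √(2 × 0.15 × 0.85 / 40) = 8.0 points. The 95% half-width is 1.96 × 8.0, about ±15.6 points.

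**Step 4: timing.** T2 runs from week 5 to week 11 after baseline. With viewing at week 3-4, T2 falls between 5 − 4 = 1 week and 11 − 3 = 8 weeks after viewing. If T2 dates are spread evenly over the window (an assumption), the share of surveys less than one month (4.34 weeks) after viewing at week v is (v + 4.34 − 5) / 6:

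- v = 3: 2.34 / 6 = 39%
- v = 4: 3.34 / 6 = 56%
- v = 1 or 2: 6% or 22%

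Section 6.1.1 ties viewing to the next clinic appointment, and section 9.1 allows for more than 30 days after baseline. The documents therefore do not fix this share.

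**Step 5: after the change.** With referrals read from the EHR in both arms and equal true rates, the difference due to patient recognition is 0 points. Recording error in the EHR may remain, but it does not depend on what the patient knows.

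**The case against.** The strongest reply is that little rests on this measure and that its bias is not shown to have a sign. Much of that stands.

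- **Direction.** A reader might infer that the survey is bound to favour mPal. The documents do not support this. They give no item wording, no PC definition shown with the item and no accuracy figures, and Step 2 shows that plausible false positives in controls reverse the sign. The stated lack of PC knowledge makes under-recognition in controls the likelier error, but no more than that.
- **Contrast in knowledge.** Controls are not wholly naive. Consent describes the intervention to both arms (section 12.1.1.1), both arms answer PC knowledge items at baseline, and the provider components are not randomised. The survey also comes some weeks after viewing. All of this may narrow the gap.
- **Timing.** A reader might also infer that T2 can never give a one-month reading. That goes too far: the nominal week 8 is 4 to 5 weeks after viewing at week 3-4. The supported statement is that T2 need not fall at one month.
- **Reach.** Referral is also read from the EHR at 3 months, no formal effectiveness hypothesis is tested, and section 10.4.3 names no test for referral proportions. The modelled bias in Step 1 lies well inside the ±15.6-point interval.

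None of this justifies the survey as the source of an arm comparison. A wide interval does not remove bias, an error of uncertain sign is a poor planning input, and dated records that do not depend on patient knowledge are already being collected.

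**Conclusion.** The point holds in a limited form. The early referral proportion is compared between arms on unblinded self-report whose accuracy may depend on the knowledge that the randomised component changes. Bias towards mPal is the more likely direction but is not proven.

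At an assumed 15% true rate, with recognition assumed at 60-80% in controls and 90-95% under mPal and no false positives, the spurious difference is about 2 to 4.5 points. Other assumed false-positive rates move it from about −2 to +11 points. The T2 window and the lack of an index date for controls add a separate weakness in definition.

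The effect is confined to one exploratory outcome and, if self-report is used there, to the knowledge-referral correlation. A reader should not infer that the referral results as a whole are compromised: the 3-month EHR outcome and the primary enrolment endpoint are untouched. The change should be made because it removes an avoidable bias at almost no cost.

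**What to change.** - In Table 2, derive both the early and the 3-month referral proportions from dated EHR referrals in both arms. This also brings Table 2 into line with section 4.1.
- Count from one index date defined identically for both arms, for example randomisation. End each window at a fixed time; for the early one this could be the nominal 8-week T2 point. The 12-month EHR release leaves room for either window.
- State that a referral means one made by the clinical team. Section 6.1.1 has the mPal patient's stated wish for PC entered in the record, and that entry should not count.
- Keep the T2 survey item as supplementary: to flag outside referrals for follow-up in the same way in both arms, and to report survey-EHR agreement by arm. Do not use it for the arm comparison.
- In section 10.4.3, name the EHR as the referral source for the correlations.

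The cost is a wording change in Table 2 and section 10.4.3. No new data are needed, and the EHR measure does not depend on T2 survey return. The small downside is that referrals outside the health system may be missed unless the survey flags them.

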#### Primary Objectives

1. Evaluate mPal’s feasibility and acceptability. We hypothesize we will be able to enroll  $\geq 60\%$  of asLC patients we approach (primary feasibility outcome), retain  $\geq 60\%$  for one-month follow-up, and achieve mean patient and provider feasibility ratings of  $\geq 3.5/5$ . For acceptability, we hypothesize we will be able to achieve mean patient and provider acceptability ratings of  $\geq 3.5/5$ . We anticipate qualitative data (n = 40 mPal patient interviews; n = 6 provider interviews) will further support the ease of use and clinical value of mPal.
2. Obtain preliminary data on effectiveness and equity outcomes for a planned trial. In line with best practices for pilot studies, we are not testing formal hypotheses for effectiveness outcomes; however, we will measure patient and provider PC knowledge and motivation and PC referrals, which we expect will improve with mPal. For equity outcomes, we will explore whether mPal appears similarly effective for patients with different characteristics (e.g., rural vs. urban, health literacy, income, race) by analyzing survey and semi-structured intervention data from mPal patients (n = 40).

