### 3 OBJECTIVES

#### PRIMARY OBJECTIVES

1. **Evaluate mPal's feasibility and acceptability.** We hypothesize we will be able to enroll  $\geq 60\%$  of asLC patients we approach (primary feasibility outcome), retain  $\geq 60\%$  for one-month follow-up, and achieve mean patient and provider feasibility ratings of  $\geq 3.5/5$ . For acceptability, we hypothesize we will be able to achieve mean patient and provider acceptability ratings of  $\geq 3.5/5$ . We anticipate qualitative data ( $n = 30-40$  mPal patient interviews;  $n = 6$  provider interviews) will further support the ease of use and clinical value of mPal.
2. **Obtain preliminary data on effectiveness and equity outcomes for a planned trial.** In line with best practices for pilot studies, we are not testing formal hypotheses for effectiveness outcomes; however, we will measure patient and provider PC knowledge and motivation and PC referrals, which we expect will improve with mPal. For equity outcomes, we will explore whether mPal appears similarly effective for patients with different characteristics (e.g., rural vs. urban, health literacy, income, race) by analyzing survey and semi-structured intervention data from mPal patients ( $n = 30-40$ ).

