#### 10.4.3 ANALYSIS OF THE SECONDARY ENDPOINT(S)

We will describe pre-post changes in the patient-reported outcome variables related to a future trial using univariate and bivariate statistics. Our chief goals will be to estimate the standard deviations of our key variables for use in planning future studies. We will examine, through the use of t-tests, whether pre-post changes in the mPal differ significantly from pre-post changes in the control group. If our intervention is successful, we would expect to see significantly greater improvement over time in our effectiveness outcomes (PC knowledge, motivation) in treatment vs. control. We will also examine correlations between changes in these measures and PC referrals; we expect changes in PC knowledge and motivation variables will be positively correlated with changes in PC referrals within both treatment and control groups.

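### The equity outcome splits mPal patients by whether knowledge rose, with no threshold, starting score or control reference, so chance and room to rise can pass for benefit

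*Combined protocol and SAP*

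**What the plan says.** Primary Objective 2 (synopsis and section 3) sets the aim: "we will explore whether mPal appears similarly effective for patients with different characteristics (e.g., rural vs. urban, health literacy, income, race"). It does this "by analyzing survey and semi-structured intervention data from mPal patients", numbering 40 in the synopsis and 30-40 in section 3. Table 2 turns the aim into a measure by comparing "Characteristics of mPal patients who do/do not seek PC referral and do/do not show knowledge increase", alongside interviews and barriers, with a schedule of T2 and three months after the intervention.

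The PC knowledge row of Table 2 describes HINTS PC as "10 items; assesses self-reported PC knowledge and PC perceptions" and also names PACKS. It gives no scoring or range for either, and does not say which one defines an increase. The schedule is "Patients: T0, T1 (mPal only), T2", so both arms have T0 and T2 scores.

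Section 10 contains no quantitative equity analysis. Section 10.4.3 asks "whether pre-post changes in the mPal differ significantly from pre-post changes in the control group", which compares arms and not characteristics. On status, Objective 2 states that "we are not testing formal hypotheses for effectiveness outcomes". On likely baseline, section 2.2 says "Most patients have poor PC knowledge", without a figure and without a breakdown by rurality, literacy, income or race.

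**The concern.** A yes/no split on whether a short, bounded score rose has three weaknesses.

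- It treats a rise of one item and a rise of six as the same.
- Some patients rise by measurement noise alone. With mPal patients only, there is no control rate to show how many.
- A patient at the maximum cannot be counted as an increase, and one near it has little room. If a characteristic goes with baseline knowledge, the split partly sorts patients by where they started.

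At stake is how the equity result is read and carried into the planned trial. A group could appear to benefit more, or two groups could appear alike, for reasons that have little to do with mPal.

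**Working it through.** The plan states no figure for the equity outcome, so there is nothing to reproduce.

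**Inputs from the documents.** Ten HINTS PC items and T0 and T2 scores in both arms (Table 2); 40 mPal patients (synopsis).

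**Assumptions.** Items are scored 0/1 and summed to 0-10. Baseline levels and learning rates are as given in each step. The characteristic divides the 40 mPal patients 20 v 20.

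**Step 1: chance rises.** With no effect, let T0 and T2 be independent binomial scores with the same probability p. Then P(increase) = (1 - P(tie))/2. At p = 0.5, P(tie) = C(20,10)/2^20 = 184,756/1,048,576 = 0.176, so P(increase) = 0.412. The same formula gives 39% at p = 0.8 and 34% at p = 0.9. If true levels vary between patients (SD 0.8 on the logit scale), simulation gives about 40% at a typical level of 50% correct and 38% at 80%. These rates are close to each other, so chance rises alone create little difference between groups. They do blur who benefited.

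**Step 2: room to rise.** If each unknown item is learned with the same probability q and nothing is forgotten, P(increase | baseline b) = 1 - (1 - q)^(10 - b). With q = 0.3:

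- b = 5: 1 - 0.7^5 = 83%
- b = 8: 1 - 0.7^2 = 51%
- b = 9: 1 - 0.7 = 30%
- b = 10: 0%

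**Step 3: equal share of the gap closed.** Using the varying-level model of step 1, take strata at about 50% and 80% correct, each closing 30% of its gap. Then 68% v 52% show an increase. Mean scores go from 5.0 to 6.5 and from 7.7 to 8.4, so raw gains are 1.5 v 0.7 points. If the high stratum closes 50% instead, 61% show an increase and the raw gain is 1.1 points. The responder rate ranks the strata as raw gain does. With low baselines of 30% v 50% and 30% closed in each, 77% v 68% show an increase, and Fisher's test rejects in about 5% of 20 v 20 samples.

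**Step 4: equal shift of 2 points** (true SD 1.5, error SD 1.0, rounded and capped at 0-10, 20 v 20 patients):

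| Subgroup means at T0 | False gap in % with increase | Chi-square rejects | Fisher rejects |
|---|---|---|---|
| 6 v 9 | 28 points | 52% | 39% |
| 5 v 8 | 14 points | 17% | 11% |
| 4 v 6 | about 1 point | 5% | 2% |
| 3 v 5 | about 0 | 6% | 2% |

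Under this model the distortion is material only when one group often starts near the top.

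**Step 5: possible replacements.** Consider first T2 adjusted for T0 within mPal patients, with no effect and strata at 50% v 80%. The T0 means differ by 7.7 - 5.0 = 2.7 points. T0 carries error, so the within-group slope is below 1, and roughly (1 - slope) x 2.7 remains as a false difference. Simulation gives +1.2 points. Since 1.2/2.7 = 0.44, the slope is about 0.56. The adjusted comparison rejects in 43% of 20 v 20 samples, against 3% for the increase split under Fisher's test. With 30% of the gap closed in both strata, the false difference is +0.84 points and rejection is 30% v 11%.

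An arm-by-characteristic contrast that uses the control patients' scores rejects in about 5% under no effect. With four cells of 20 and an SD of change s, its standard error is s x sqrt(4/20) = 0.447s. The 95% half-width is 1.96 x 0.447s = 0.88s.

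**The case against.** The strongest reply is that the rule is barely specified. Table 2 is a list of measures, an increase is left undefined, and the 0-10 score is an assumption. This stands in part: no any-rise rule is written down. But the two-way split is written down, and nothing in section 10 replaces it. A minimum rise would cut chance increases and leave even less room for high scorers.

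A second reply is that section 2.2 expects poor knowledge in most patients, so few would start near the ceiling. This stands. A reader might infer that the split will make rural or low-literacy patients look better, or will reverse the equity conclusion. The documents do not support that. They do not link any characteristic to baseline knowledge, and the reversal in step 3 appears only if the share of the gap closed is taken as the true effect. On raw points the high stratum did gain less (0.7 or 1.1 against 1.5).

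A third reply is that the outcome is exploratory, no test is tied to it, and the same row uses referral and interviews. This also stands and limits the consequence. It does not supply the missing control reference or the missing subgroup summary.

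**Conclusion.** The concern holds in a limited form. The increase/no-increase split is a weak basis for the equity outcome. It discards information, and it counts as improved about 37-40% of patients who would rise with no effect, a rate that an mPal-only analysis cannot show. It can also favour a lower-starting group when the other starts near the maximum. The false gap ranges from about 0-1 point to 28 points in step 4, depending on baselines that the documents do not give. Its size and direction in this trial are therefore unknown.

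All figures rest on an assumed 10-item summed score and assumed baselines, effects and 20 v 20 groups. The primary endpoint, enrollment, is unaffected. The change is a cheap improvement to an exploratory outcome and does not correct a flaw in the main result. A reader might also infer that adjusting for T0 within mPal patients would solve the problem. Step 5 shows that it can do worse than the split.

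**What to change.** In the Equity row of Table 2, replace the increase/no-increase split with knowledge as a continuous score, and name the instrument and its scoring. Add one or two sentences to section 10.4.3:

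- For each characteristic and each arm, report mean T0, mean T2 and mean change with 95% CIs, and the percentage at the maximum score at T0.
- Give a descriptive arm-by-characteristic contrast in change, with its CI.
- Do not base the equity conclusion on T0-adjusted comparisons of characteristics within mPal patients alone.

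State also which score counts as T0 when the knowledge section is repeated before a late mPal viewing (section 9.1), since that can happen only in the mPal arm.

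The cost is one table row and a few lines of text; no new data are needed. There are three downsides. There is no simple responder percentage to quote or to use in choosing interview contrasts. Intervals will be wide, with a half-width of about 0.88 SD of change at 20 per cell. A score cap can still distort the contrast: in step 3, closing 30% of the gap in both strata gives 0.7 - 1.5 = -0.8 points against unchanged controls. This is why the share at maximum should be reported beside it.
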